Specific Aim 4: Examine the predictors of long-term adherence to the Tai Chi exercise program by assessing the relationship between baseline demographic, health, functional, and psychosocial subject characteristics, which are being collected in the trial, with subsequent adherence to the intervention. We will quantify adherence by the number of Tai Chi sessions attended and will determine the characteristics of those most likely to complete the program.

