Informed consent will be obtained at the first study visit. The Project Director or Research Assistant will review the details of the study and will review the entire informed consent document with the participant, either by asking the participant to follow along as the document is read or by having the document read to them. After each section of the consent form, the participant will be asked if he/she has any questions. Once the staff is confident that the participant understands all aspects, the participant will be asked to sign the form and will be given a copy to keep. The participant will be given the contact information of the study team members and be encouraged to call at any time for any additional questions that may occur during the participant's participation in the trial. Informed consent will be obtained in a private place in the housing facility in which the potential participant resides, either their own apartment, or another identified private location within the facility.

The participant will be allowed to take as much time as they would like to decide about their participation in the study and may discuss the study with anyone that they wish before making a decision to participate. Only participants capable of providing individual consent will be enrolled in the study.

FOR THE FOCUS GROUP AND THE WITHDRAWAL GROUP, WE WILL RECEIVE THEIR VERBAL CONSENT.

6.7 Withdrawal of participants (anticipated circumstances when participants will be withdrawn without their consent, how participants will be withdrawn, including use of any collected data and follow-up with any new/pertinent information):

The criteria for discontinuing a participant's participation include any life-threatening or potentially disabling event, including hemodynamic collapse, stroke, transient ischemic attack, dysrhythmia, renal insufficiency, angina, myocardial infarction, anaphylaxis, acute hemorrhage, or hospitalization for acute illness. If the participant recovers from a potentially serious event, he/she may re-enter the study if they are assessed safe to return. In this situation, we will ask the participant's primary MD to assess the participant's medical fitness to return to the study. To do this, we will send the attached letter to the participant's MD with the participant's permission, and request that the MD sign off that it is medically safe for the participant to resume their participation in the study.

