PARTICIPANTS WHO HAVE BEEN ENROLLED IN WAVE 2, PAIR 3, WILL BE WITHDRAWN FROM THE STUDY, DUE TO THE DECISION OF THE NIA TO STOP THE TRIAL. THESE PARTICIPANTS HAVE COMPLETED A BASELINE ASSESSMENT BUT WERE NEVER ENROLLED IN THE STUDY INTERVENTION. A LETTER OF EXPLANATION TO BE SENT TO THESE PARTICIPANTS IS ATTACHED. FOR PARTICIPANTS ENROLLED IN WAVE 2, PAIRS 1 AND 2, IN WHICH THE INTERVENTIONS WERE UNDERWAY, THE INTERVENTIONS WILL BE STOPPED, AND PARTICIPANTS WILL RECEIVE A LETTER OF EXPLANATION, ATTACHED.

6.8 If the participants may have diminished capacity to provide informed consent or to understand study procedures (now or in the foreseeable future), describe additional safeguards to protect their rights and welfare, including how and when you will engage legally authorized representatives:

Only participants capable of providing individual consent will be enrolled in the study. To be sure the subject is capable of providing informed consent, we will briefly screen volunteers for their cognitive capacity before enrolling them and will accept those who can recall at least 2 of 3 words in 3 minutes and 2 of 3 key elements of the study protocol. For participants with little or no formal education we will read the informed consent form with a family member present if the participant wishes, and an appropriate witness (the housing sites have a care advisor/social services advisor on site who can serve as the witness) . For individuals with little or no formal education, we will ask participants to answer the following questions to assess their understanding and assure they are informed.

1. Can you tell me in your own words what this study is about, and what is involved if you participate? 2. Is the study voluntary or do you have to participate? If you choose to participate, do you have to stay in the study until it ends or can you withdraw whenever you would like or need to? 3. Are there any benefits to you for participating in the study? (If yes, can you explain the benefits?) Are there any risks to you for participating in the study? (If yes, can you explain the risks?) 4. Have you had enough time to make your decision to participate? 5. Do you have any questions about the study? 6. Please explain how you will contact the study staff if you have any questions or problems during the study.

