7 STUDY PROCEDURES

7.1 Study visits including procedures/tests involved (e.g., blood test, x-rays, questionnaires. If numerous study visits and procedures are involved, include a study procedure timeline):

The participant's Housing Site will be assigned by random, such as the flip of a coin, to participate in either a Tai Chi or Health and Wellness Activity study group. The participant will be asked to take part in whatever group his/her housing site has been assigned. Participants in the Tai Chi Activity group will be asked to attend for one hour twice a week for twelve months, or a total of 96 classes. Participants in the Health and Wellness Activity group will be asked to attend for one hour, once a month for a total of 12 classes.

Study Groups: The Tai Chi study group will be led by a certified Tai Chi instructor. It will consist of warm-up exercises, stretches, and Tai Chi movements developed for use with older adults. The participant will be asked to attend all of the classes in the assigned study group over the one year period. He/She may also be asked to watch and follow along with a Tai Chi instructional video in his/her apartment at his/her convenience one or two times each week for 15-30 minutes. If he/she does not have a video player, one will be provided

to use during your study enrollment. The video will consist of warm-ups, seated stretches, and simplified Tai Chi movements. The participant will be asked to keep a log of practice dates and times and bring this to class with them for review with the instructor, and will be regularly collected. The Health and Wellness Activity study group will also be led by a trained instructor. Activities will include lectures and discussions on healthcare topics of interest to older adults. All sessions will take place in a common room of the housing facility. The instructors will have access to water for participants and a phone in case of emergency. **PARTICIPANTS WHO ENROLLED IN WAVE 2, PAIR 3 WILL NOT TAKE PART IN EITHER OF THE STUDY INTERVENTIONS.**

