Assessments: Participants will be asked to complete an assessment described below on 3 separate occasions. The first assessment will occur before beginning the assigned activity group of either Tai Chi exercise sessions or Health and Wellness sessions, twice a week for one year. The second assessment will occur six months (+/- 3 weeks) after beginning the sessions and the third assessment will occur twelve months (+/- 3 weeks) after beginning the sessions. (Wave 2, participants from Housing site pairs 1 and 2, participation will end following the second assessment at six months. These participants will not be asked to complete a third assessment at twelve months. This is due to the recent decision by the NIA and DSMB to stop the study intervention at this time. Only these Wave 2 site pairs will have reached the point of the six month assessment at the time that the study intervention is stopped.) It will take about two hours to complete each of these three assessments. A trained research assistant will carry out the assessments which will take place in the participant's apartment or a private place at the housing facility.

1. **Health Interview** - At each of the three assessments, the participant will be asked questions about his/her health, medications, history of falls, whether he/she has had any hospitalizations or emergency room visits. Height, weight, blood pressure and heart rate will be measured. Participants will be asked questions about daily activities, mood, sleep, memory and balance.

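### Aim 4 counts Tai Chi sessions attended without a denominator, although Wave 2 sites were offered only about half the planned classes

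*Combined protocol and SAP*

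**What the plan says.** Specific Aim 4 (section 4) examines which baseline demographic, health, functional and psychosocial characteristics predict long-term adherence. On measurement it says "We will quantify adherence by the number of Tai Chi sessions attended", and it adds that the investigators "will determine the characteristics of those most likely to complete the program". It gives no denominator and does not define completion.

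Section 7.1 sets the planned exposure: Tai Chi residents are asked to "attend for one hour twice a week for twelve months, or a total of 96 classes".

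The stop was written into other sections. For Wave 2, pairs 1 and 2, section 6.7 refers to sites "IN WHICH THE INTERVENTIONS WERE UNDERWAY, THE INTERVENTIONS WILL BE STOPPED". Section 7.1 says of the same residents that "participation will end following the second assessment at six months", and places that visit as follows: "The second assessment will occur six months (+/- 3 weeks) after beginning the sessions". Wave 2 pair 3 had a baseline assessment but no classes, and section 6.7 withdraws it. Wave 1 ran the full year: section 8.1 reports an interim analysis on its 12-month data.

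Section 8.1 sets out analyses for Aims 1 and 2 only. It contains no offset, wave or site term, censoring rule or population for Aim 4. Its 50% attendance threshold belongs to the Aim 1 per-protocol analysis and is itself averaged over the full year.

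**The concern.** A raw count measures adherence only if everyone has the same number of classes to attend. Once one wave is cut to about half, the count reflects two things: how willingly a resident came, and how many classes the trial held. The second is a decision of the trial. For completion the problem is absolute, because no Wave 2 resident could finish a 12-month program.

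Aim 4 is meant to show who sustains a year-long exercise program. If the waves or sites differ in community, age, health or ethnicity, those traits can look like predictors of adherence when they only mark the sites that were stopped. If the waves do not differ, the count is still noisier than it need be and real predictors are harder to find.

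**Working it through.** **1. The plan's own figure.** Two classes a week for 48 weeks (12 months of 4 weeks) gives 2 × 48 = 96, which matches section 7.1. Using 52 weeks would give 104, so 96 implies 48 class weeks.

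**2. Classes offered in Wave 2, pairs 1 and 2.** The documents give no class count at the stop. Section 7.1 says these sites will have reached the six-month assessment when the intervention is stopped, and that visit has a window of ±3 weeks. I apply the window to the stop itself, which is an assumption.

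| Weeks of classes | Classes offered (2 × weeks) | Share of 96 |
|---|---|---|
| 23 (26 − 3) | 46 | 48% |
| 24 (half of 48) | 48 | 50% |
| 26 | 52 | 54% |
| 29 (26 + 3) | 58 | 60% |

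Full attendance in Wave 2 therefore scores 46 to 58, the same as a Wave 1 resident who attended 48% to 60% of classes.

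**3. How much of the count is wave.** Assumptions not in the documents:
- 16 sites split equally between two waves, half of them Tai Chi, with 20 residents per site;
- hence 4 × 20 = 80 Tai Chi residents in Wave 1 and 2 × 20 = 40 in Wave 2 pairs 1 and 2;
- the same attendance fraction in both waves, Beta(2.1, 0.9), with mean 0.70 and variance 2.1 × 0.9 / (3² × 4) = 0.0525.

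With m classes offered in Wave 2:
- between-wave variance = (2/3)(1/3) × [0.70 × (96 − m)]²
- within-wave variance = 0.0525 × [(2/3) × 96² + (1/3) × m²]

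For m = 46: between = (2/9) × 35.0² = 272.2; within = 322.6 + 37.0 = 359.6; share = 272.2 / 631.8 = 43%.

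For m = 58: between = (2/9) × 26.6² = 157.2; within = 322.6 + 58.9 = 381.4; share = 157.2 / 538.7 = 29%.

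The within-wave SD is √0.0525 × 96 = 22 sessions in Wave 1, but only 10.5 to 13.3 in Wave 2. At 48 classes offered, simulation with SD 20% gave a share of 22% for mean attendance of 40% and 54% for 80%.

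**4. Completion.** On the same assumed sizes, 40 of 120 residents who started classes (33%) cannot complete, whatever they do.

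**5. Does this create false predictors?** A simulation assumed 80 and 40 residents, 48 classes offered in Wave 2, attendance mean 60% and SD 25% in both waves, and a baseline factor unrelated to attendance. It gave these rates of p < 0.05:

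| Difference in the factor between waves | Raw count | Attended / offered |
|---|---|---|
| none | 5% | 5% |
| 0.3 SD | 13% | 5% |
| 0.5 SD | 28% | 5% |

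The false signal appears only when the factor differs by wave. The simulation has no site effects and no decline in attendance over time.

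**6. A wave term on the raw count is not enough.** A trait that raises attendance by 10 percentage points adds 0.10 × 96 = 9.6 sessions in Wave 1 but 0.10 × 48 = 4.8 in Wave 2. A wave intercept removes the shift in means but not this difference in scale.

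**The case against.** The strongest reply is that Aim 4 is a secondary, descriptive aim about long-term adherence to a year-long program, and only Wave 1 was offered a year. A Wave 1 analysis is then the natural reading. The revised timeline for data analysis mentioned in section 5.2 is an attachment that cannot be checked here. This lowers the weight of the point. It does not settle it, because no current text restricts Aim 4 to Wave 1.

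Three stronger readings are tempting, and the documents do not support them.

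- **That the stop must generate false predictors.** It acts on whole sites. The documents report no baseline difference between waves, and step 5 shows no excess where there is none. Wave's share of the variance is not itself bias in any predictor.
- **That poor health will predict low adherence only because the protocol suspended people.** Sections 6.7 and 10.3 do discontinue residents after listed health events. But section 6.7 also says "If the participant recovers from a potentially serious event, he/she may re-enter the study if they are assessed safe to return", and no number or duration of discontinuations is given. People with such events would largely miss classes anyway, and absence through illness is arguably part of what Aim 4 asks. Removing it changes the estimand.
- **That pair 3 enters as zeros.** These residents are withdrawn and had no intervention to adhere to. The plan need only say that they are outside the Aim 4 data set.

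A further fair objection is to the simple remedy. A proportion over six months is not comparable with one over twelve if attendance declines with time. That objection stands, and the fix takes it up.

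**Conclusion.** The point holds as a defect of measurement. Aim 4's stated rule works only with equal exposure, and the trial stop removed equal exposure without a matching change to the rule. Two consequences need only the documents and a stop near six months: full attendance in Wave 2 pairs 1 and 2 scores about 46 to 58 of 96, and completion there is impossible.

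The size of the distortion in the predictors is not known. The 29% to 43% share of variance rests on assumed wave sizes and 70% mean attendance. The false-positive rates in step 5 apply only if baseline traits differ between waves. Without such differences, the effect is added noise. The change should be made before Aim 4 is analysed. No primary inference depends on it.

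**What to change.** 1. Define adherence as sessions attended out of sessions offered at the resident's site up to its stop date. Use a binomial model, or a count model with the log of sessions offered as offset, with wave and site terms.
2. Compare or pool waves only over a common window, the first six months. Otherwise analyse 12-month adherence in Wave 1 only.
3. Define completion. Analyse it in Wave 1 only, or replace it with time to voluntary drop-out, censored at the stop date.
4. State that pair 3 is not in the Aim 4 data set.
5. Report protocol-required discontinuations descriptively as a reason for non-attendance, and remove those intervals only in a sensitivity analysis. The lists in sections 6.7 and 10.3 differ (10.3 adds syncope and injurious non-accidental falls) and must be reconciled before these intervals are coded.

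**Cost.** This needs a short addition to section 8.1 and one derived variable. Section 11.1 lists class attendance data and section 10.3 says the discontinuation events are recorded. The documents do not say that classes held per site, or dates of suspension and re-entry, are recorded, so this should be confirmed. The price is a shorter observation period for Wave 2, a smaller sample for completion (80 rather than 120 on the assumed sizes), and site effects estimated from few Tai Chi sites (six on those sizes).

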5 STUDY DESIGN								
5.1	
Study design (e.g., double-blind, placebo-controlled, parallel design): We will address our aims by conducting a cluster randomized controlled trial (RCT) of twice weekly group Tai Chi exercise sessions plus self-practiced video-directed supplemental sessions vs. an organized healthy aging educational program plus monthly social telephone calls, in low income senior housing facilities located within three diverse communities surrounding Boston. This is a pragmatic trial, rather than a comparative effectiveness or mechanistic study, which aims to determine the functional and health care utilization outcomes of Tai Chi compared to one's customary daily practices, while controlling for attention through the educational sessions. The added focus group sessions and withdrawal interviews are designed as a qualitative and descriptive study.
							
5.2	
Study duration (total): The study duration is expected to be 5 years in total.
 
A REVISED STUDY TIMELINE FOR COMPLETION OF FIELD ACTIVITIES AND DATA ANALYSIS IS ATTACHED.
							
5.3	
Duration of study for participants: Participants will be enrolled for about 26 months; The baseline assessment will occur within 4 weeks of the telephone screen; the study intervention of Tai Chi or health aging educational program sessions will last for 12 months; followed by a follow up assessment to occur within 4 weeks of completing the study intervention (a midpoint assessment will occur at 6 months from the start of the intervention). Participant visits will end at the follow up assessment, but Health Care Utilization data will be collected for the one year during the study intervention, and for one year following the completion of the intervention.
 
For each of the group (Tai Chi or health educational program), we will conduct three 30-45 min. focus groups, one within the first four months of the intervention, one within the second four months of the intervention, one within the last four months of the intervention.
 
For those who withdraw from the study, we will conduct individual interviews as close to the time of drop-out as possible.
							
6 PARTICIPANT SELECTION AND WITHDRAWAL								
6.1	
Source of study participants: Participants will be individuals aged > or = 60, living in a participating senior housing site
							
6.2	
Total target number of participants to be enrolled: 320
 
  
 Facility/Institution	Unit (if applicable)	Number of Participants	
   
 Senior Supportive Housing in Boston, Brookline, Somerville and Lynn MA		Approximately 20 participants per site will be enrolled in 16 sites.	
  
		Facility/Institution	Unit (if applicable)	Number of Participants	Senior Supportive Housing in Boston, Brookline, Somerville and Lynn MA		Approximately 20 participants per site will be enrolled in 16 sites.
Facility/Institution	Unit (if applicable)	Number of Participants						
Senior Supportive Housing in Boston, Brookline, Somerville and Lynn MA		Approximately 20 participants per site will be enrolled in 16 sites.						

6.3	
Inclusion criteria: These include: living in low income senior housing facilities, age > or = 60, able to understand instructions in English, able to participate safely in Tai Chi exercises at least twice a week, expected to remain in the facility for 1 year,
 
Inclusion criteria for the focus group: any participant stays in the study.
 
Inclusion criteria for the withdrawal group: any participant drops off from the study.
		
6.4	
Exclusion criteria: Exclusion criteria will be: already participating in Tai Chi exercises, any unstable or terminal illness (e.g., unstable cardiovascular disease, active cancer, unstable COPD, advanced dementia, psychosis), inability to maintain posture sitting or standing, and the inability to hear, see, or understand Tai Chi instructions and assessment questions. We will briefly screen volunteers for their cognitive capacity over the telephone and accept those who can recall at least 2 of 3 words in 3 minutes, and 2 of 3 highlighted elements of the study protocol.
		
6.5	
Participant recruitment (describe recruitment methods and submit any materials to be used to recruit participants): This study calls for recruiting 320 elderly individuals living in 16 subsidized senior housing facilities. The facility managers have all agreed to cooperate with this study, provide us with access to their residents, inform them about the study, and encourage participation. In addition, we will post information promoting the study, conduct public information sessions in each facility, place notices in all resident mailboxes and newsletters, and inform residents that they will be visited personally by research staff. We have contracted with the Center for Survey Research of the University of Massachusetts-Boston (CSR) to conduct door-to-door recruitment by having trained interviewers speak directly with potential study participants. CSR has experienced interviewers who are themselves older adults and can relate to and establish trust from older adult populations. Using similar door-to-door recruiting, CSR helped us recruit 765 seniors > 70 years of age from the local Boston metropolitan area for the MOBILIZE Boston study between 2006-2008.
 
Subjects will be recruited and studied in 2 waves. Recruitment will occur during the first 6 months of each wave. If a resident agrees to participate, the recruiter will conduct a brief screen for inclusion and exclusion criteria. If the volunteer passes the screen, their baseline assessment will be scheduled as soon as possible.
 
WE WILL INTRODUCE THE FOCUS GROUP DURING THE REGULAR SESSION FIRST. WE WILL THEN SEND OUT AN INTRODUCTORY MAIL FOLLOWED BY A PHONE INVITATION TO RECRUIT THE PARTICIPANTS.
 
FOR THOSE WITHDRAWAL FROM THE CLASS, WE WILL SEND OUT AN INTRODUCTORY MAIL FOLLOWED BY A PHONE INVITATION TO RECRUIT THE DROP-OUTS.
		

RECRUITMENT FOR THE STUDY IS NOW DISCONTINUED, AS DETERMINED BY THE NIA, FOLLOWING THE DSMB MEETING AND FOLLOW UP DISCUSSIONS OF 10/25/17.

6.6 Procedures for obtaining informed consent, including who will obtain consent and the timing of consent from recruitment:

Informed consent will be obtained at the first study visit. The Project Director or Research Assistant will review the details of the study and will review the entire informed consent document with the participant, either by asking the participant to follow along as the document is read or by having the document read to them. After each section of the consent form, the participant will be asked if he/she has any questions. Once the staff is confident that the participant understands all aspects, the participant will be asked to sign the form and will be given a copy to keep. The participant will be given the contact information of the study team members and be encouraged to call at any time for any additional questions that may occur during the participant's participation in the trial. Informed consent will be obtained in a private place in the housing facility in which the potential participant resides, either their own apartment, or another identified private location within the facility.

The participant will be allowed to take as much time as they would like to decide about their participation in the study and may discuss the study with anyone that they wish before making a decision to participate. Only participants capable of providing individual consent will be enrolled in the study.

FOR THE FOCUS GROUP AND THE WITHDRAWAL GROUP, WE WILL RECEIVE THEIR VERBAL CONSENT.

6.7 Withdrawal of participants (anticipated circumstances when participants will be withdrawn without their consent, how participants will be withdrawn, including use of any collected data and follow-up with any new/pertinent information):

The criteria for discontinuing a participant's participation include any life-threatening or potentially disabling event, including hemodynamic collapse, stroke, transient ischemic attack, dysrhythmia, renal insufficiency, angina, myocardial infarction, anaphylaxis, acute hemorrhage, or hospitalization for acute illness. If the participant recovers from a potentially serious event, he/she may re-enter the study if they are assessed safe to return. In this situation, we will ask the participant's primary MD to assess the participant's medical fitness to return to the study. To do this, we will send the attached letter to the participant's MD with the participant's permission, and request that the MD sign off that it is medically safe for the participant to resume their participation in the study.

PARTICIPANTS WHO HAVE BEEN ENROLLED IN WAVE 2, PAIR 3, WILL BE WITHDRAWN FROM THE STUDY, DUE TO THE DECISION OF THE NIA TO STOP THE TRIAL. THESE PARTICIPANTS HAVE COMPLETED A BASELINE ASSESSMENT BUT WERE NEVER ENROLLED IN THE STUDY INTERVENTION. A LETTER OF EXPLANATION TO BE SENT TO THESE PARTICIPANTS IS ATTACHED. FOR PARTICIPANTS ENROLLED IN WAVE 2, PAIRS 1 AND 2, IN WHICH THE INTERVENTIONS WERE UNDERWAY, THE INTERVENTIONS WILL BE STOPPED, AND PARTICIPANTS WILL RECEIVE A LETTER OF EXPLANATION, ATTACHED.

6.8 If the participants may have diminished capacity to provide informed consent or to understand study procedures (now or in the foreseeable future), describe additional safeguards to protect their rights and welfare, including how and when you will engage legally authorized representatives:

Only participants capable of providing individual consent will be enrolled in the study. To be sure the subject is capable of providing informed consent, we will briefly screen volunteers for their cognitive capacity before enrolling them and will accept those who can recall at least 2 of 3 words in 3 minutes and 2 of 3 key elements of the study protocol. For participants with little or no formal education we will read the informed consent form with a family member present if the participant wishes, and an appropriate witness (the housing sites have a care advisor/social services advisor on site who can serve as the witness) . For individuals with little or no formal education, we will ask participants to answer the following questions to assess their understanding and assure they are informed.

1. Can you tell me in your own words what this study is about, and what is involved if you participate? 2. Is the study voluntary or do you have to participate? If you choose to participate, do you have to stay in the study until it ends or can you withdraw whenever you would like or need to? 3. Are there any benefits to you for participating in the study? (If yes, can you explain the benefits?) Are there any risks to you for participating in the study? (If yes, can you explain the risks?) 4. Have you had enough time to make your decision to participate? 5. Do you have any questions about the study? 6. Please explain how you will contact the study staff if you have any questions or problems during the study.

